2.3 PHARMACOKINETIC OBJECTIVE

The endpoints will be analyzed separately for the three cohorts: Cohort A (1.5 mg/kg QW), Cohort B (3 mg/kg Q2W), and Cohort C (6 mg/kg Q4W).

The PK objective for this study is to characterize the exposure (C_{trough}) of emicizumab in patients receiving 1.5 mg/kg QW, 3 mg/kg Q2W, and 6 mg/kg Q4W prior to drug administration on Day 1 and at the following timepoints:

- Every week during Weeks 1–4 on emicizumab
- Every 2 weeks during Weeks 5–9 on emicizumab
- Every 4 weeks during Weeks 13–37 on emicizumab
- Every 8 weeks during Weeks 41–49 on emicizumab
- Every 12 weeks from Week 57 thereafter while continuing on emicizumab, until the end of the study
- Additional PK samples will be taken in patients who require up-titration (see schedule of assessments in [Appendix 1](#))

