The initial maintenance dose of 1.5 mg/kg QW was evaluated by the Study BH29992 JMC during an interim data review (clinical cutoff date: 28 October 2016). As enrollment occurred faster than anticipated, the two planned data review meetings were combined into one. All available data (including safety, efficacy, and pharmacokinetics) from the first 20 patients enrolled in Cohort A was assessed by the JMC to determine the appropriateness of the starting maintenance dose, as well as to decide whether the study could begin enrolling patients <2 years of age. On 7 December 2016, the JMC recommended continuing enrollment of patients in Cohort A at the maintenance dose of 1.5 mg/kg QW, as well as to open enrollment to patients <2 years of age at that same maintenance dose. Since exposure at 1.5 mg/kg QW was similar between patients 3–12 years of age and adolescent/adult patients, the up-titration scheme for children has been modified to be the same as the one used in adolescent/adult patients, that is, individual up-titration to 3 mg/kg QW should they experience suboptimal control of bleeding on emicizumab (see Section 4.5.2).

Furthermore, two Phase III studies investigating 3 mg/kg Q2W (BH30071) and 6 mg/kg Q4W (BO39182) have been initiated in adolescent/adult patients with hemophilia A without inhibitors (BH30071) and with and without inhibitors (BO39182). All three dosing regimens are predicted to achieve similar exposure (in terms of steady-state average concentration, $C_{\text{avg},\text{ss}}$; see Table 2), and despite higher peak concentrations and lower trough concentrations with less frequent dosing regimens, all are expected to result in similar treatment response (all three dosing regimens provide

similar predicted ABR distribution) and safety profiles. Of note, the exposures achieved with these three dosing regimens remain well below the safe and well-tolerated one achieved with the highest dose of 3 mg/kg QW (observed trough concentration of $120 \pm 26.8 \mu\text{g/mL}$). Ultimately, these three dosing regimens will provide the option for patients to receive emicizumab at different scheduled intervals, while still delivering the same cumulative dose.

Table 2 Simulated Median Pharmacokinetic Parameters

Parameters	Maintenance Dose		
	1.5 mg/kg QW	3 mg/kg Q2W	6 mg/kg Q4W
$C_{max,ss}$ ($\mu\text{g/mL}$)	54.6	56.8	63.4
$C_{trough,ss}$ ($\mu\text{g/mL}$)	51.5	48.0	40.7
$C_{avg,ss}$ ($\mu\text{g/mL}$)	53.0	53.1	53.0

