4.5.2 Dosage, Administration, and Compliance

Emicizumab treatment will begin with a loading dose of 3 mg/kg QW for the first 4 weeks (Day 1 of each week) followed on Week 5 by a maintenance dose of either 1.5 mg/kg QW (Cohort A), 3 mg/kg Q2W (Cohort B), or 6 mg/kg Q4W (Cohort C). Note that the cumulative dose studied in all three cohorts is identical, but the dose administration schedule differs between cohorts. Patients will receive prophylactic emicizumab for a minimum of 52 weeks, or until unacceptable toxicity or discontinuation from the study due to any cause.

On 7 December 2016, the JMC recommended continued enrollment to Cohort A at the original starting maintenance dose of 1.5 mg/kg QW, and to open enrollment to patients < 2 years of age at that same maintenance dose. Moreover, review of data in adults and adolescents from two ongoing Phase III studies evaluating emicizumab at 3 mg/kg Q2W (BH30071) and 6 mg/kg Q4W (BO39182) has identified no safety concerns to date. See Section 3.3.1.1 for details.

During the 52-week treatment period, individual patients may have their dose up-titrated if they experience suboptimal bleeding control on emicizumab. *Patients in Cohorts A, B, or C with ≥ 2 qualifying bleeds within a 12-week interval may have the opportunity to have their maintenance emicizumab dose increased to 3 mg/kg QW starting on Week 17, if they receive approval from the Medical Monitor. Of note, for patients from Cohorts B or C who have a dose up-titration, their dosing regimen will change from Q2W or Q4W to QW. Qualifying bleeds are defined as spontaneous and clinically significant, physician verified (e.g., with diagnostic imaging, clinical examination, photograph), and occurring while on prophylactic emicizumab at steady-state on the maintenance dose (after Week 5). Should patients meet protocol-defined criteria for up-titration, the investigator will contact the Medical Monitor to initiate a discussion about possible up-titration. Upon up-titration to the new maintenance dose of 3 mg/kg QW, the patient's schedule of assessments will reset to Week 1, and the next five visits must take place at the site.*

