Details on the devices to be used for study medication withdrawal from the vial and SC injection are provided in the Pharmacy Manual.

Emicizumab will be administered as a SC injection in the home setting after a period of in-clinic administration and training. The first five drug administrations must be performed in a monitored setting such as an infusion center, clinic, or hospital, with a 60-minute observation period following each of the first three doses. For patients with a previous history of a clinically significant hypersensitivity reaction, additional precautions as described in Section 5.1.1.2 should be considered. The fourth and fifth scheduled study drug administrations must also be performed in the monitored setting, and the patient/caregiver will be trained and have the opportunity to ask any questions to the HCP before the scheduled start of home administration. The patient (≥ 7 years of age)/caregiver will observe at least one SC injection performed by the HCP and successfully administer at least one SC injection while being observed by the HCP prior to starting home administration. Each site will have the discretion to provide additional training if deemed appropriate. If, despite additional training, the investigator determines that the patient/caregiver is unable to inject emicizumab correctly, then arrangements may be made to identify a trained caregiver or HCP to administer the SC injections.

Patients/caregivers will be provided with the clinic contact information, to use in case they have questions related to self-administration between visits.

Medication administration errors during training will be recorded and competence of the patient or caregiver to administer at home will be documented in the electronic Case Report Form (eCRF). If necessary, patients/caregivers or their HCP may choose to continue administration of study drug in the clinic. Compliance in the home setting is to be monitored by recording emicizumab administration on an electronic, handheld device and recording collected used and unused vials during each patient's clinic visit.

Study medication should be administered on the scheduled dosing day. On days when trough plasma PK samples are to be collected, patients will be dosed after those samples are drawn.

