2.3.4 Pharmacokinetic Endpoint

The pharmacokinetic (PK) endpoint for this study is the exposure (C_{trough}) of emicizumab in patients receiving 1.5 mg/kg QW, 3 mg/kg Q2W, and 6 mg/kg Q4W, assessed prior to drug administration on Day 1 and at the following timepoints:

- Every week during Weeks 1-4 on emicizumab
- Every 2 weeks during Weeks 5-9 on emicizumab
- Every 4 weeks during Weeks 13-37 on emicizumab
- Every 8 weeks during Weeks 41-49 on emicizumab
- Every 12 weeks from Week 57 thereafter while continuing on emicizumab until the end of the study.

Additional PK samples will be taken in patients who require up-titration.

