4. STATISTICAL METHODS

For continuous variables, means, medians, ranges, and standard deviations will be presented. For categorical variables, the number and percentage of patients within each category will be presented. For each variable (continuous or categorical), the number of available observations will be reported. No formal hypothesis testing will be performed as the study is entirely descriptive.

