4.5 PHARMACOKINETIC ANALYSES

For all patients, pre-dose (trough) plasma concentrations of emicizumab will be presented descriptively at each timepoint by dose group, including arithmetic and geometric means, median, range, standard deviations, and coefficients of variation.

Nonlinear mixed effects modeling will be used to analyze the dose-concentration-time data of emicizumab following SC administration. Population PK parameters, such as clearance and volume of distribution, will be estimated, and the influence of various covariates, such as age and body weight, on these parameters will be investigated graphically. Secondary PK parameters, such as area under the curve, will be derived from individual post-hoc predictions. Data may be pooled with data from previous Phase I/II studies and Study BH29884. These analyses will be reported in a dedicated report.

In addition, region- and/or country-specific analyses will be performed to support regulatory submissions as needed (e.g., PK analysis in Japanese vs. non-Japanese patients or analyses based on ethnicity).

The PK will be analyzed separately for the three cohorts: Cohort A (1.5 mg/kg/QW), Cohort B (3 mg/kg/ Q2W), and Cohort C (6 mg/kg Q4W).

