Appendix 2 Schedule of Assessments (cont.)

- ^q Patients are advised to inform the investigator about adverse events at every visit. Adverse events will be reported on the eCRF by the investigator. Injection-site reaction adverse events will be collected on a separate form from the adverse event form. If there is unexpected worsening of the patient's hemophilia in terms of severity (e.g., increased number of doses of bypassing agents to stop bleeds compared with before study entry), frequency of bleeds, or nature at any time during the study, this should be documented as an adverse event on the Adverse Event eCRF, conveying that the underlying condition has changed by including applicable descriptors (e.g., "increased clinical severity of hemophilia").
- ^r Drug accountability will not be performed at the first visit of emicizumab receipt. Drug dispensation will not occur at the study completion/early termination visit. *Note: for Cohort C, there are visits where emicizumab is not administered per schedule.*
- ^s Haemo-QoL-Short Form (children 8 years of age and older) assessed on an electronic, handheld device by patients during patient's visit in clinic prior to emicizumab injection at Weeks 1, 13, 25, 37, 49, every 24 weeks from Week 57, and study completion/early termination.
- ^t Proxy assessment of HRQoL and aspects of caregiver burden using the Adapted InhibQoL Including Aspects of Caregiver Burden questionnaire for all children assessed on electronic, handheld device by caregivers during patient's visit in clinic prior to emicizumab injection at Weeks 1, 13, 25, 37, 49, every 24 weeks from Week 57 and study completion/early termination.
- ^u Emicizumab concentration. Plasma samples for this assessment should be taken prior to emicizumab injection.
- ^v PD biomarkers will be measured at a central laboratory. See [Appendix 3](#), for detailed explanation of PD biomarker assessments. Blood samples may also be drawn to conduct biomarker assays at the central laboratory on an unscheduled basis (at the clinical judgment of the investigator) at any time.

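### Week 7 is listed as a C_trough timepoint for all three regimens, but in Cohort C (6 mg/kg Q4W) it falls halfway between doses, so that sample is not a trough

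*SAP*

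**What the plan says.** SAP 2.3.4 names a single PK endpoint, C_trough, for 1.5 mg/kg QW, 3 mg/kg Q2W and 6 mg/kg Q4W. It is assessed before drug administration on one list of weeks shared by the three regimens. One line of that list is "Every 2 weeks during Weeks 5-9 on emicizumab". Protocol 2.3 has the same line: "Every 2 weeks during Weeks 5–9 on emicizumab".

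For the analysis, SAP 4.5 states that "pre-dose (trough) plasma concentrations of emicizumab will be presented descriptively at each timepoint by dose group". It makes no exception for any cohort or week.

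On dosing, Protocol 4.5.2 has four weekly loading doses, "followed on Week 5 by a maintenance dose of either" 1.5 mg/kg QW, 3 mg/kg Q2W or 6 mg/kg Q4W. The same section says that on days when trough samples are collected, "patients will be dosed after those samples are drawn".

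The schedule of assessments (SAP Appendix 2, repeated from Protocol Appendix 1) applies to Cohorts A, B and C and has a PK sample at Week 7. Footnote r is attached to that cell and notes that "for Cohort C, there are visits where emicizumab is not administered per schedule". Footnote u, on the same row, still asks for the PK sample to be taken before the injection.

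**The concern.** A trough is the concentration just before the next dose. With maintenance starting at Week 5 and given every four weeks, Cohort C has no Week 7 dose for a sample to precede. If SAP 2.3.4 and 4.5 are programmed as written, the trough table will show a mid-interval concentration in the Cohort C column at Week 7.

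The error would run against the expected pattern. Protocol 3.3.1.1 expects similar average exposure across regimens "despite higher peak concentrations and lower trough concentrations with less frequent dosing regimens". The Week 7 row would instead show the least frequent regimen with the highest apparent trough. It would also sit above the 45 µg/mL trough target of Protocol 3.3.1, although the simulated steady-state trough for Q4W in Protocol Table 2 is 40.7 µg/mL. A reader could take that row as early evidence that Q4W troughs in children are higher than they are.

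**Working it through.** The plan gives no figure to reproduce here. The point rests on the calendar (step 1); steps 2 and 3 only indicate size.

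**1. Calendar check**

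- PK weeks (SAP 2.3.4): 1–4; 5, 7, 9; 13, 17, 21, 25, 29, 33, 37; 41, 49; then 57, 69 and every 12 weeks after.
- Dosing weeks (Protocol 4.5.2): loading in Weeks 1–4 for everyone. From Week 5, Cohort A is dosed every week, Cohort B at Weeks 5 + 2k and Cohort C at Weeks 5 + 4k (k = 0, 1, 2, …).

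| Cohort | Listed PK weeks with no dose |
|---|---|
| A (QW) | none |
| B (Q2W) | none |
| C (Q4W) | Week 7 only |

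There are 12 listed weeks from Week 5 to Week 49, and Cohort C is dosed in 11 of them. Week 57 and every twelfth week after also fit, since 57 = 5 + 4×13 and 12 is a multiple of 4. Week 7 is two weeks after the Week 5 dose: day 14 of 28.

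**2. Illustrative size**

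Assumption: a one-compartment model with first-order absorption.

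- Average concentration: 53.0 µg/mL (Protocol Table 2, simulated), giving CL/F = 1.5/(7 × 53.0) = 0.00404 L/day/kg.
- Half-life: 4–5 weeks, so 28–35 days (Protocol 1.2, single SC dose).
- V/F = CL/F × half-life / ln 2 = 0.163 L/kg (28 days) to 0.204 L/kg (35 days).
- Absorption rate ka: 0.3–0.8/day. This is an assumption; the documents give no value.
- Doses: 3 mg/kg on days 0, 7, 14 and 21, then the cohort's maintenance regimen from day 28. Week 7 is day 42 and Week 9 is day 56.

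Pre-sample concentrations (µg/mL):

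| Half-life (days), ka (/day) | C, Week 7 | C, Week 9 | C: Week 7 / Week 9 | A, Week 7 | B, Week 7 | C/A, Week 7 | C/A, Week 9 |
|---|---|---|---|---|---|---|---|
| 28, 0.3 | 65.1 | 46.5 | 1.40 | 51.5 | 51.2 | 1.26 | 0.90 |
| 28, 0.8 | 62.2 | 44.0 | 1.41 | 50.1 | 48.8 | 1.24 | 0.88 |
| 35, 0.3 | 57.5 | 43.9 | 1.31 | 45.8 | 45.8 | 1.25 | 0.93 |
| 35, 0.8 | 55.5 | 42.1 | 1.32 | 44.9 | 44.1 | 1.24 | 0.91 |

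The Week 7 value is 31–41% above the next true trough. Cohort C reads 24–26% above Cohort A at Week 7 but 7–12% below it at Week 9. It is also above Cohort B at Week 7 in every row.

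As a check, the model's steady-state Q4W trough is 37.9–42.5, against 40.7 in Table 2. Fitting the model freely to all nine Table 2 values (half-life 32 days, ka 0.46/day, all within about 1%) gives Cohort C 59.4 at Week 7 and 44.0 at Week 9, a ratio of 59.4/44.0 = 1.35.

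**3. Against sampling noise**

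The one observed trough spread in the documents is 120 ± 26.8 µg/mL at 3 mg/kg QW (Protocol 3.3.1.1). Reading ± as a standard deviation, the CV is 26.8/120 = 22%. If Cohort C were similar (assumption), the standard error of a mean of 10 children would be 22%/√10 = 7%. A 31–41% shift is several times that.

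**The case against.** The strongest reply is that the SAP already flags the exception at the cell concerned. Footnote r is attached to the Week 7 PK entry, so anyone working from the schedule knows Cohort C is not dosed. The words pre-dose in SAP 4.5 and the Protocol 4.5.2 description of a trough day could then be read as keeping the sample out of the summary. This shows the visit was planned knowingly, and the sample may well be wanted. But the footnote neither drops nor relabels the value. A silent exclusion also conflicts with SAP 2.3.4, which lists Week 7 as a C_trough timepoint for the Q4W regimen by name, and with SAP 4.5, which covers each timepoint.

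A second reply is that the list is a sampling schedule under a loose heading. Week 1 precedes any drug, and the samples up to Week 5 reflect loading only, so they are not troughs of the Q4W regimen either. That is fair. Those samples are still drawn before a dose in every cohort, so the pre-dose label is true of them. At Week 7 in Cohort C it is not.

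Third, little depends on it. The SAP says "No formal hypothesis testing will be performed as the study is entirely descriptive", the cohorts are analysed separately, and the 45 µg/mL interim review concerned Cohort A and ended in December 2016. The population PK model uses dose-concentration-time data and can take the sample at its true time, where a day-14 value is informative. All of this stands and limits the importance of the point. So does the caution that the concentrations above come from assumed absorption rates and simulated medians.

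**Conclusion.** The point holds as a minor error in the wording of the endpoint and its summary. By the calendar alone, the Cohort C Week 7 sample is mid-interval, yet SAP 2.3.4, Protocol 2.3 and SAP 4.5 treat it as a trough. It is the only such week in any cohort.

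Under the stated model assumptions the mislabelled value would be roughly a third higher than the next true trough, and it would reverse the expected order of the regimens at that week. Changing the assumptions would alter the size but not the fact that the sample is not a trough.

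The effect is confined to one timepoint in about 10 children. Later troughs and the population PK analysis are unaffected, and no decision rule uses the value. It is still worth correcting because C_trough is the only PK endpoint SAP 2.3.4 names.

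**What to change.** In SAP 2.3.4, add a sentence saying that Week 7 is not a C_trough timepoint for Cohort C, because no dose is given that week. Under SAP 4.5, report the Cohort C Week 7 result as a mid-interval concentration (day 14 of 28), outside the trough summary, and keep it in the population PK model. Leave all other weeks, and Cohorts A and B, unchanged. Every remaining Cohort C timepoint is then a true pre-dose sample.

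The cost is one sentence and one row label. No sample is added, dropped or moved, and the Week 7 value is still reported. Protocol 2.3 can be aligned at the next amendment.

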2.3.5 Safety Objectives and Endpoints

Safety parameters to be measured include exposure, adverse events (AEs; including serious AEs [SAEs]; AEs of special interest [AESI], AEs leading to drug discontinuation, and deaths), clinical laboratory values and abnormalities (including hematology, coagulation, chemistry, and anti-emicizumab antibodies), vital signs, ECG, and concomitant medication use.

2.3.6 Biomarker Objectives and Endpoints

Biomarker parameters to be measured include but are not limited to coagulation-related assays such as aPTT, PT/INR, D-dimer, and FVIII activity assays.

2.4 DETERMINATION OF SAMPLE SIZE

The sample size for this study is based on feasibility and clinical considerations rather than statistical considerations, taking into account the number of pediatric patients with hemophilia A with inhibitors available for participation in this trial. Hence, at least 40 children younger than 12 years of age and up to approximately 80 patients with hemophilia A and FVIII inhibitors who are currently receiving treatment with bypassing agents will be enrolled in this study: approximately 60 patients in Cohort A with allowance of patients 12-17 years of age who weigh < 40 kg at the time of informed consent and with allowance for approximately 5 additional patients < 2 years of age in Cohort A - and approximately 10 patients each in Cohort B and Cohort C.

During the study, a re-assessment of the initially specified sample size based on enrolment consideration may be performed. This may result in an increase in sample size, if necessary, to expand the safety database.

2.5 ANALYSIS TIMING

The primary analysis will be performed 52 weeks after the last patient in the primary population of Cohort A has been enrolled or withdrawn prematurely, whichever occurs

first. The primary population of Cohort A consists of all patients who will receive emicizumab at 1.5 mg/kg QW enrolled prior to the close of enrollment for patients ≥ 2 years of age (up to approximately 60 patients) and is used to define the timing of the primary analysis. If no patients < 2 years of age are included in the primary population of Cohort A, the final analysis will still occur at the specified time; however, enrolment in the study may be left open exclusively for patients < 2 years of age in order to enroll up to 5 such patients.

The final analysis will occur at the end of the study as defined in the protocol. Additional updates may be performed between the primary and final analysis as requested by Health Authorities or deemed necessary by the Sponsor.

Timing of interim analyses is detailed in Sections [3.1](#) and [4.9](#).

3. STUDY CONDUCT

3.1 DATA MONITORING

A Joint Monitoring Committee (JMC) composed of selected internal Sponsor members (Pediatric Medical Specialist, Safety Scientist, Clinical Pharmacologist, and Statistician) constituting the Internal Monitoring Committee and external pediatric hemostasis/thrombosis experts (including an external Clinical Pharmacology expert) will be in place throughout the duration of the study. Internal Monitoring Committee members have been selected on the basis that they have no contact with the sites as part of their responsibilities. The external pediatric hemostasis/thrombosis experts function to enhance safety monitoring, leverage external experts' scientific expertise by providing advice on data interpretation, and serve as a consultative body to the Sponsor.

If a majority of the initial 3-5 patients, aged ≥ 2 to < 12 years, treated for a minimum of 12 weeks require up-titration or if their plasma emicizumab trough concentrations do not meet a target of 45 $\mu\text{g}/\text{mL}$, the JMC may suggest adaptation of the starting maintenance dose. Thus, in a first interim data review, all cumulative data (e.g., safety, efficacy, and pharmacokinetics) will be evaluated by the JMC to provide recommendations of changing the starting maintenance dose for the subsequent patients to be enrolled.

Once at least 10 patients, aged ≥ 2 to < 12 years, have been dosed for a minimum of 12 weeks, a second interim data review of all available data (e.g., safety, efficacy, and pharmacokinetics) will be conducted to draw study and/or dosing recommendations produced by the JMC and to allow children from < 2 years of age to participate. As a result of this interim data review, further adjustments to the maintenance dose may also be made, if necessary. The JMC may, if needed, monitor patient safety at pre-specified intervals and ad hoc as needed throughout the study.

If rapid study enrolment occurs and the fifth and tenth patient are enrolled within 2 weeks of each other, the two data review meetings may be combined and take place at the same time.

The evaluation of the interim data reviews will be performed on the efficacy endpoints – number of bleeds over time –as well as on the safety and PK results.

Specific operational details, such as committee composition, member roles and responsibilities, frequency, and timing of meetings and interim data review are detailed in a separate JMC Agreement.

Of note, because patient recruitment occurred faster than anticipated, the first and second interim data reviews were combined into one interim data review. Following the interim review on 7 December 2016, the JMC recommended that enrolment to Cohort A could continue with the selected maintenance dose of 1.5 mg/kg QW and that the Cohort A of the study should be opened for recruitment of children < 2 years of age.

